1. INTRODUCTION

INCB 18424-303 is a randomized, vehicle-controlled study in adolescent and adult (≥ 12 years old) participants with AD eligible for topical therapy. Approximately 600 participants will be randomized 2:2:1 to ruxolitinib 0.75% cream BID, ruxolitinib 1.5% cream BID, or vehicle cream. In addition, approximately 20% of the overall study population will consist of adolescents. Participants with baseline IGA score of 2 will constitute up to approximately 25% of the overall study population. Participants with AD involvement of 3% to 20% BSA and IGA score of 2 to 3 will receive blinded study treatment for 8 weeks followed by a randomized 44-week LTS extension period. In the LTS period, participants initially randomized to vehicle will receive either ruxolitinib 0.75% or 1.5% cream BID.

The purpose of this SAP is to provide details of the statistical analyses that have been outlined in the study Protocol. The scope of this plan will be executed by the Department of Biostatistics or designee, and the analyses of PK will be executed by the Department of Clinical Pharmacokinetics or designee.

Another Phase 3 study, INCB 18424-304, has the identical study design as INCB 18424-303. This SAP applies to both INCB 18424-303 and INCB 18424-304 studies.

2. STUDY INFORMATION, OBJECTIVES, AND ENDPOINTS

2.1. Protocol and Case Report Form Version

This SAP is based on INCB 18424-303 and -304 Protocol Amendment 2 dated 13 FEB 2019 and CRFs approved 05 MAR 2019. Unless superseded by an amendment, this SAP will be effective for all subsequent Protocol amendments and CRF versions.

2.2. Objectives and Endpoints

[Table 1](#) presents the objectives and endpoints.

Table 1: Objectives and Endpoints

Objectives	Endpoints
Primary	
To establish the efficacy of ruxolitinib cream in participants with AD.	
 • Proportion of participants achieving IGA-TS at Week 8.^a
Key Secondary	
To further assess the treatment effects of ruxolitinib cream.	
 • Proportion of participants who achieve EASI75 at Week 8.^a • Proportion of participants with a \geq 4-point improvement in Itch NRS score from baseline to Week 8. • Proportion of participants with a clinically meaningful (\geq 6-point) improvement in the PROMIS Short Form – Sleep Disturbance (8b – 24-hour recall) score at Week 8. • Proportion of participants with a clinically meaningful (\geq 6-point) improvement in the PROMIS Short Form – Sleep-Related Impairment (8a – 24-hour recall) score at Week 8.
Secondary	
To evaluate the safety and tolerability of ruxolitinib cream.	The frequency and severity of AEs; physical examinations; vital signs; and laboratory data for hematology, serum chemistry, and urinalysis.
To further evaluate efficacy of ruxolitinib cream.	
 • Proportion of participants achieving an IGA-TS at Weeks 2 and 4. • Proportion of participants achieving an IGA of 0 or 1 at each visit. • Proportion of participants with a \geq 4-point improvement in Itch NRS score from baseline to Weeks 2 and 4. • Proportion of participants who achieve EASI50 at each visit during the VC period. • Proportion of participants who achieve EASI75 at Weeks 2 and 4. • Proportion of participants who achieve EASI90 at each visit during the VC period. • Mean percentage change from baseline in EASI score at each visit during the VC period. • Mean percentage change from baseline in SCORAD score at each visit during the VC period. • Change from baseline in Itch NRS score at each visit during the VC period. • Time to achieve Itch NRS score improvement of at least 2, 3, or 4 points. • Change from baseline in Skin Pain NRS score at each visit during the VC period.

Table 1: Objectives and Endpoints (Continued)

Objectives	Endpoints
To further evaluate efficacy of ruxolitinib cream.	
• Proportion of participants with a clinically meaningful (\geq 6-point) improvement in the PROMIS Short Form – Sleep-Related Impairment (8a) and Sleep Disturbance (8b) 24-hour recall score at Weeks 2 and 4.• Change from baseline in PROMIS Short Form – Sleep-Related Impairment (8a) 24-hour recall and Short Form – Sleep Disturbance (8b) 24-hour recall score at Weeks 2, 4, and 8.• PROMIS Short Form – Sleep-Related Impairment (8a) 7-day recall and Short Form – Sleep Disturbance (8b) 7-day recall score at Weeks 8, 12, 24, and 52.• Change from baseline in AD afflicted %BSA at every visit.
To evaluate the participants' Quality of Life and other patient-reported outcomes.	
• Change from baseline in POEM score at each visit.• Change from baseline in DLQI score at Weeks 2, 4, 8, 12, 24, and 52 and at unscheduled visits.• Mean PGIC score at Weeks 2, 4, and 8.• Proportion of participants with each score on the PGIC at Weeks 2, 4, and 8.• Proportion of participants with a score of either 1 or 2 on the PGIC at Weeks 2, 4, and 8.• Change from baseline in EQ-5D-5L score during the VC period.• Change from baseline in WPAI:SHP v2.0 at Weeks 2, 4, 8, 12, 24, 36, and 52.
To evaluate the PK of ruxolitinib cream in plasma.	
• Trough plasma concentrations of ruxolitinib at all study visits.

[figure not shown]
For an EMA submission, if applicable, the primary endpoint is changed to the proportion of participants who achieve EASI75 at Week 8, and the first key secondary endpoint is changed to the proportion of participants achieving IGA-TS at Week 8.

3. STUDY DESIGN

This is a randomized, vehicle-controlled study in adolescent and adult (≥ 12 years old) participants with AD eligible for topical therapy. Approximately 600 participants will be randomized 2:2:1 to ruxolitinib 0.75% cream BID, ruxolitinib 1.5% cream BID, or vehicle cream. In addition, approximately 20% of the overall study population will consist of adolescents. Participants with baseline IGA score of 2 will constitute up to approximately 25% of the overall study population. Participants with AD involvement of 3% to 20% BSA and IGA score of 2 to 3 will receive blinded study treatment for 8 weeks followed by a randomized, double-blinded, 44-week LTS extension period. In the LTS period, participants initially randomized to vehicle will receive either ruxolitinib 0.75% or 1.5% cream BID.

The study schema is shown below in [Figure 1](#). All participants will have follow-up assessments 30 (+ 7) days after the last application of study drug.

Figure 1: Study Design Schema

*At week 8 (LTS baseline), participants initially on vehicle will be randomized to either Rux 1.5% or 0.75% cream BID. Additionally, to qualify for the LTS period, the IGA score of 0 to 4 and %BSA of 0% to 20% will be required.

3.1. Randomization

In the treatment period, approximately 600 participants will be randomized 2:2:1 to ruxolitinib 0.75% cream BID, ruxolitinib 1.5% cream BID, or vehicle cream. Participants will be stratified at randomization based on baseline IGA (2, 3) and region (North America or other).

3.2. Control of Type I Error

For the primary and key secondary endpoints, the overall 2-sided Type I error is 0.05.

A graphical procedure with gatekeeping testing strategy for the primary and key secondary analyses, as specified in Protocol Section 10.3, will be implemented to control the overall Type I error. The underlying procedure is derived using the methodology developed in Bretz et al (2009). The method will guarantee a strong control of the family-wise error rate.

In Step 1, two families of 8 elementary hypotheses tests are grouped according to treatment comparison between each ruxolitinib cream group to vehicle group, where

- Family 1 (1.5% BID vs vehicle):
 - H11: proportion of participants who achieve IGA-TS;
 - H12: proportion of participants who achieve EASI-75;
 - H13: proportion of participants with a ≥ 4 -grade improvement in Itch NRS over baseline;
 - H14: proportion of participants with a ≥ 6 -point improvement in the PROMIS Sleep Disturbance score.
- Family 2 (0.75% BID vs vehicle):
 - H21: proportion of participants who achieve IGA-TS;
 - H22: proportion of participants who achieve EASI-75;
 - H23: proportion of participants with a ≥ 4 -grade improvement in Itch NRS over baseline;
 - H24: proportion of participants with a ≥ 6 -point improvement in the PROMIS Sleep Disturbance score.

Step 2 has one family of 2 hypotheses tests:

[figure not shown]
- Family 3 (1.5% BID vs vehicle and 0.75% BID vs vehicle on PROMIS Sleep-Related Impairment score):
 - H31: Proportion of participants with a clinically meaningful improvement (≥ 6 -point change over baseline) in Sleep-Related Impairment (8a) score between 1.5% BID vs vehicle;
 - H32: Proportion of participants with a clinically meaningful improvement (≥ 6 -point change over baseline) in Sleep-Related Impairment (8a) score between 0.75% BID vs vehicle.

To control the overall Type I error rate, 2-sided $\alpha = 0.05$, the Bonferroni's method will be used. In Step 1, within Family 1 and 2, the endpoints are tested in a fixed sequence at Bonferronized 2-sided $\alpha = 0.025$ level. The endpoint will be tested only if the associated primary (and secondary in previous steps) are rejected. For any dose level, if the 4 related null hypotheses can be rejected, then the fixed sequence for the other dose level can be conducted at 2-sided $\alpha = 0.05$ level. If all null hypotheses in Family 1 and 2 are rejected, in Step 2, H31 and H32 will be tested using Bonferroni- Hochberg's procedure with overall 2-sided $\alpha = 0.05$ level. The approach is visualized in [Figure 2](#).

[figure not shown]
For an EMA submission, if applicable, the primary endpoint is changed to the proportion of participants who achieve EASI75 at Week 8, and the first key secondary endpoint is changed to the proportion of participants achieving IGA-TS at Week 8, and the hypotheses are changed accordingly.

Figure 2: Control of the Overall Type I Error Rate

Step 1:

Step 2:

3.3. Sample Size Considerations

Approximately 600 participants will be randomized 2:2:1 to ruxolitinib 0.75% BID, 1.5% BID, or vehicle and stratified by baseline IGA (2, 3) and region (North America or Europe). The sample size calculation is based on the Fisher exact test for the statistical comparison on the primary efficacy endpoint. The Fisher exact test is used to provide a conservative evaluation of statistical power, and it is accurate when there is a small expected number of responders in the vehicle group. Based on the results from a Phase 2, randomized, dose-ranging study (INCB 18424-206), the IGA-TS at Week 8 is assumed to be 45% and 30% for active arms (1.5% BID and 0.75% BID, respectively) versus 10% for placebo. Using a 2-sided alpha of 0.025, the sample size will have $> 95\%$ power to detect a difference between each of the 2 active treatment groups versus vehicle. In addition to provide adequate power for efficacy variables, the sample size is determined to provide an adequate database for safety evaluation.

3.4. Schedule of Assessments

Refer to Protocol Amendment 2 dated 13 FEB 2019 for a full description of all study procedures and assessment schedules (Protocol Tables 3 and 4) for this study.

4. DATA HANDLING DEFINITIONS AND CONVENTIONS

4.1. Scheduled Study Evaluations and Study Periods

4.1.1. Day 1

Day 1 is the date that the first application of ruxolitinib cream or vehicle cream is administered to the participants in the specific period.

For randomized participants not treated with any study drug, Day 1 is defined as the day of randomization.

4.1.2. Study Day

If a visit/reporting date is on or after Day 1, then the study day at the visit/reporting date will be calculated as

Day # = (Visit/Reporting Date – Day 1 date + 1).

If the visit/reporting date is before Day 1, then the study day at the visit/reporting date will be calculated as

Day # = (Visit/Reporting Date – Day 1 date).

A study day of -1 indicates 1 day before Day 1.

4.1.3. Baseline Value

Baseline is the last nonmissing measurement obtained before or on the day of first application of ruxolitinib cream or vehicle cream.

For participants who cross-over treatment in LTS period, baseline is the last nonmissing measurement obtained before or on the day of first application of study treatment in LTS period.

For randomized participants not treated with any study drug, baseline is defined as the last nonmissing assessment before or on the day of randomization for all parameters.

When scheduled assessments and unscheduled assessments occur on the same day and time of the assessment or time of first application is not available, use the following convention to determine baseline:

- If both a scheduled and an unscheduled visit are available on the day of the first application and the time is missing, use the scheduled assessment as baseline.
- If all scheduled assessments are missing on the day of the first application and an unscheduled assessment is available, use the unscheduled assessment as baseline.

4.1.4. Last Available Value

The last available value is the last nonmissing measurement obtained after starting ruxolitinib cream or vehicle cream and within 30 days after the last application of ruxolitinib cream or vehicle cream, or before the first application of ruxolitinib cream in the next period, whichever is earlier.

4.1.5. Handling of Missing and Incomplete Data

For response endpoints, all nonresponders, as well as all participants who are missing postbaseline values, will be defined as nonresponders for the NRI analysis.

For continuous endpoints, any participant who is missing postbaseline values may have missing data handled using MMRM under the missing-at-random assumption. MMRM model implicitly adjusts for missing data through a variance-covariance structure.

For other endpoints, missing observations will be handled as detailed in the specific sections addressing each analysis.

4.2. Variable Definitions

4.2.1. Body Mass Index

Body mass index (BMI) will be calculated as follows:

$$\text{BMI (kg/m}^2\text{)} = [\text{weight (kg)}] / [\text{height (m)}]^2$$

4.2.2. Prior and Concomitant Medication

Prior medication is defined as any nonstudy medication started before the first application of study treatment.

Concomitant medication is defined as any nonstudy medication that is started accordingly:

- Before the date of first application of study treatment and is ongoing throughout the study or ends on/after the date of first application of study treatment.
- On/after the date of first application of study treatment and is ongoing or ends during the course of study treatment.

A prior medication could also be classified as "both prior and concomitant medication" if the end date is on or after the first application of study treatment. In the listing, it will be indicated whether a medication is prior-only, concomitant-only, or both prior and concomitant.

For the purposes of analysis, all medications will be considered concomitant medications unless the medications can unequivocally be defined as not concomitant.

5. STATISTICAL METHODOLOGY

5.1. General Methodology

Unless otherwise noted, SAS® software (SAS Institute Inc, Cary, NC; Version 9.1 or later) will be used for the generation of all tables, graphs, and statistical analyses. Descriptive summaries for continuous variables will include, but not be limited to, the number of observations, mean, standard deviation, median, minimum, maximum, 1st quartile, 3rd quartile and 95% CI. Descriptive summaries for categorical variables will include the number and percentage of participants in each category.

5.2. Treatment Groups

This is a randomized, double-blinded vehicle-controlled study followed by a LTS extension period. Data will be summarized based on treatment regimen that was assigned (ITT) or that the participant actually applied (safety).

During the VC period, the treatment groups will be 1.5% BID, 0.75% BID, and Vehicle.

During the LTS period, the treatment groups will be 1.5% BID, 0.75% BID, Vehicle to 1.5% BID, and Vehicle to 0.75% BID.

5.3. Analysis Populations

5.3.1. Intent-to-Treat Population

All participants who are randomized to the study constitute the ITT population. Treatment groups for this population will be defined according to the treatment assignment at the time of randomization regardless of the actual study treatment the participant might apply during his/her participation in the study.

The ITT population will be used for the summary of demographics, baseline characteristics, participant disposition, and analyses of all efficacy data.

5.3.2. Per Protocol Population

Participants in the ITT population who are considered to be sufficiently compliant with the Protocol compose the PP population, which is defined for supportive sensitivity analyses for efficacy endpoints in the treatment period. Participants with important protocol deviations, as defined in Section 6.3, will be excluded from the PP population.

5.3.3. Safety Population

All randomized participants who applied at least 1 application of ruxolitinib cream or vehicle cream will constitute the safety population. Treatment groups for this population will be determined according to the actual treatment the participant applied on Day 1 regardless of assigned study treatment.

All safety analyses will be conducted using the safety population.

5.3.4. Pharmacokinetic/Pharmacodynamic Evaluable Population

The PK/PD evaluable population will include all participants who applied at least 1 application of ruxolitinib cream and provided at least 1 postdose plasma sample (1 PK/PD measurement) that complies with the instruction in the Protocol. Participants in whom it is not possible to obtain a blood sample for PK/PD from an area of the body that was not treated with (exposed to) study drug (eg, due to difficulties of technical/ procedural nature) will not be included in the PK/PD evaluable population because of the material risk of the contamination of such a sample with study drug from the skin through which a needle is passed. The study pharmacokineticist will review data listings of study drug application and sample records to identify participants to be excluded from PK data analyses. The study research investigator will review data listings of PD data and sample records to identify participants to be excluded from analyses of PD data.

6. BASELINE, EXPOSURE, AND DISPOSITION VARIABLES AND ANALYSES

[Appendix A](#) provides a list of planned tables, figures, and listings. Sample data displays are included in a separate document.

6.1. Baseline and Demographics, Physical Characteristics, and Disease History

6.1.1. Demographics

The following demographics will be summarized for the ITT population during the VC period: age, age group, sex, race, ethnicity, region, weight, height, and BMI.

6.1.2. Baseline Disease Characteristics

Baseline disease characteristics summarized for the ITT population during the VC period include but are not limited to the following:

- Time since first onset of AD
- Prior history of asthma (No/Yes)
- Prior allergies (food, environmental) (No/Yes)
- History of contact dermatitis (No/Yes)
- Common complications of AD
- Prior treatments for AD
- Time since onset of current AD
- Prior therapy for AD given in the past 30 days (No/Yes)
- Total %BSA involvement in current AD episode
- Facial involvement (No/Yes)
- Number of AD episodes/flare-ups over the last 12 months

- Baseline IGA score (2, 3)
- Baseline EASI score

6.1.3. Medical History

For participants in the ITT population during the VC period, medical history will be summarized by assigned treatment groups. This summary will include the number and percentage of participants with medical history for each body system/organ class as documented in the eCRF.

6.2. Disposition of Participants

The number and percentage of participants who were randomized, treated, and completed the VC period; were treated in the LTS period; completed the LTS period; discontinued the treatment or withdrew from the study during the VC period; and discontinued treatment or withdrew from the study during the LTS period with a primary reason for discontinuation will be summarized for the ITT population during the VC and LTS periods.

6.3. Protocol Deviations

In general, the following are important protocol deviations that may significantly affect the primary and gated secondary analyses:

- Missing data for the primary endpoint;
- Overall application compliance less than 60%;
- Key inclusion/exclusion criteria deviations;
- Use of restricted or prohibited medications.

Participants with one or more such deviations will be excluded from the PP population.

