2.2.2.4. Efficacy of Ruxolitinib Cream

2.2.2.4.1. Atopic Dermatitis

INCB 18424-206 (see [Figure 3](#)) was a Phase 2, randomized, vehicle- and active (TC 0.1% cream)-controlled dose-ranging study in participants with AD. The study was double-blinded for vehicle, ruxolitinib doses, and active control. A total of 307 participants were randomized equally to ruxolitinib 1.5% cream BID, 1.5% QD, 0.5% QD, and 0.15% QD; vehicle BID; and active control (TC 0.1% cream BID) and stratified by EASI score (≤ 7 and > 7). Participants received blinded study drug for 8 weeks, and those who were randomized to TC applied triamcinolone 0.1% cream BID for 4 weeks and vehicle cream for the following 4 weeks, so as to not exceed the allowable triamcinolone application duration. Participants then were permitted to enter an open-label extension and apply ruxolitinib 1.5% cream BID for an additional 4 weeks.

Figure 3: INCB 18424-206 Study Schema

In total, 307 participants were randomized to one of the 6 treatment groups in the double-blind period of the study. Of these, 260 participants completed the 8-week double-blind therapy and 46 discontinued for a variety of reasons, including adverse event (n = 3), lack of efficacy (n = 1), lost to follow-up (n = 13), noncompliance with study drug (n = 5), physician decision (n = 2), pregnancy (n = 1), protocol deviation (n = 1), and withdrawal by subject (n = 20).

The primary endpoint was mean percentage change from baseline in the EASI score at Week 4.

- Mean percentage change from baseline EASI score at dose 1.5% BID showed 71.6% improvement at Week 4 (primary endpoint), as compared with 15.5% vehicle ($p < 0.0001$), and 78.5% improvement at Week 8, as compared with 26.9% vehicle ($p < 0.0001$).

EASI50/75/90 and IGA response results showed all strengths to be efficacious and statistically superior to vehicle. In addition, efficacy was time- and regimen-related, with 1.5% QD and 1.5% BID numerically greater than the other treatment groups including TC.

All cream strengths continued to demonstrate improvement through Week 8 (Note: TC was only for 4 weeks).

- 1.5% ruxolitinib cream BID was shown to be noninferior to TC on mean EASI (Week 4).
- 1.5% ruxolitinib cream BID was more efficacious than TC by IGA response at Week 4: 38% versus 25.5% ($p < 0.001$), respectively.

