6.6.2. Restricted Medications and Procedures

The following are permitted during the study under specified conditions:

- Use of any over-the-counter, nonprescription preparations (including vitamins, minerals, and phytotherapeutic, herbal, or plant derived preparations) within 7 days before the baseline visit through the follow-up visit, unless deemed acceptable by the investigator.
- Use of any prescription medication (including immunizations, phytotherapeutic, herbal, or plant-derived preparations) within 7 days before the baseline visit through the follow-up visit, unless deemed acceptable by the investigator.
- Bleach baths are allowed as long as they do not exceed 2 baths per week and their frequency remains the same throughout the study.
- Participants should not take baths or showers within 2 hours after study drug application.
- Topical anti-infectives or other topical treatments applied to active AD lesions should not be used for at least 4 hours before and 2 hours after application of study drug.

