6.6.3. Prohibited Medications and Procedures

The following are not permitted during the study:

- Any investigational medication other than the study drug.
- Topical corticosteroids, tacrolimus, pimecrolimus, and PDE4-inhibitors (Eucrisa®).
- Other topical agents for AD (except bland emollients as noted in Section [6.6.1](#)).
- Treatment known to affect the course of AD.
- Systemic corticosteroids, methotrexate, cyclosporine A, azathioprine and biological therapies, or other immunosuppressant agents.
- Allergen immunotherapy
- Phototherapy or tanning beds.
- Live or live-attenuated vaccination.

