10. STATISTICS

10.1. Sample Size Determination

Approximately 600 participants will be randomized 2:2:1 to ruxolitinib 0.75% BID, 1.5% BID, or vehicle and stratified by baseline IGA (2, 3) and region (North America or other). The sample size calculation is based on the Fisher exact test for the statistical comparison on the primary efficacy endpoint. The Fisher exact test is used to provide a conservative evaluation of statistical power, and it is accurate when there is a small expected number of responders in the vehicle group. Based on the results from a Phase 2, randomized, dose-ranging study (INCB 18424-206), the IGA-TS at Week 8 is assumed to be 45% and 30% for active arms (1.5% BID and 0.75% BID, respectively) versus 10% for placebo. Using a 2-sided alpha of 0.025, the sample size will have > 95% power to detect a difference between each of the 2 active treatment groups versus vehicle. In addition to provide adequate power for efficacy variables, the sample size is determined to provide an adequate database for safety evaluation.

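### The SAP's nonresponder rule omits the Protocol's discontinuation clause and ignores prohibited AD treatment, so a Week 8 success after such treatment counts as a response

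*SAP*

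**What the plan says.** **Nonresponse.** SAP 4.1.5 (all response endpoints) and SAP 7.2.2 (primary analysis) recognise two routes: an observed nonresponse, or a missing postbaseline value. SAP 7.3.2 gives the key secondary endpoints similar models. Protocol 10.4.1 has a further route: stopping study treatment before the timepoint, or leaving the study for any reason. SAP 10.1 lists three changes to the Protocol's analyses (the LTS evaluable population, duration of AEs, and sleep-related impairment as a key secondary endpoint). The narrower nonresponder rule is not among them.

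**Prohibited treatment.** Protocol 6.6.3 bars, among other things, "Topical corticosteroids, tacrolimus, pimecrolimus, and PDE4-inhibitors". Protocol 6.5.2 lists AD worsening that needs a prohibited medicine among the criteria for permanent discontinuation of study drug. SAP 6.3 names "Use of restricted or prohibited medications" as an important deviation, and SAP 5.3.2 gives the consequence: "Participants with important protocol deviations, as defined in Section 6.3, will be excluded from the PP population". The same section describes the PP set as supportive.

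**Restricted treatment.** Protocol 6.6.2 introduces its list with "The following are permitted during the study under specified conditions".

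**Sizing.** Protocol 10.1 sets the allocation: "Approximately 600 participants will be randomized 2:2:1 to ruxolitinib 0.75% BID, 1.5% BID, or vehicle". The planned Week 8 IGA-TS rates are 45% on 1.5%, 30% on 0.75% and 10% on vehicle. The power claim reads: "Using a 2-sided alpha of 0.025, the sample size will have > 95% power to detect a difference".

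**The concern.** Under the Protocol, AD worsening that needs a prohibited medicine is a ground for stopping study drug, and stopping before Week 8 is nonresponse. The SAP breaks the second link without saying so. Neither document has a rule for a participant who takes a prohibited AD treatment and stays on study drug.

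Skin that clears with the help of a topical corticosteroid can therefore be credited to the randomised cream. The other planned analyses do not correct this. Multiple imputation, last observation carried forward and the tipping point analysis (SAP 7.2.4) deal with missing values, and the PP analysis removes these users instead of scoring them as failures.

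At stake are the estimated response rates, odds ratios and confidence intervals, and some power for the 0.75% dose. Under SAP 3.2 all eight hypotheses in Families 1 and 2 must be rejected before Step 2 opens, so a failure in the 0.75% sequence would also close the tests of sleep-related impairment.

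**Working it through.** **1. Who is affected.** Take participants who use a Protocol 6.6.3 AD treatment before Week 8:

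| Situation at Week 8 | Protocol 10.4.1 | SAP 4.1.5 / 7.2.2, ITT |
|---|---|---|
| Value missing | nonresponder if discontinued | nonresponder |
| Observed nonresponse | nonresponder | nonresponder |
| On study drug, observed success | no clause applies: responder | responder |
| Stopped study drug early, observed success | nonresponder | responder, if the value is used as Week 8 |

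The gap is the last two rows. The last row can arise because Protocol 7.1.2 and 8.7 ask for an EOT visit on stopping, and Protocol Table 3 puts Week 8 and EOT in one column. I found no SAP rule on whether an early EOT value may stand for Week 8. This route matters mainly for IGA and EASI: the itch and sleep diaries end with treatment in the vehicle-controlled period (Protocol 8.2.7).

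**2. The plan's own power.** 600 at 2:2:1 gives 600 × 2/5 = 240 per active arm and 600 × 1/5 = 120 on vehicle. Exact two-sided Fisher power at 0.025, by full enumeration:
- 45% v 10%: above 99.99%.
- 30% v 10%: 98.9%.

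Both meet the stated figure of more than 95%.

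**3. Illustration for ITT.** Assumptions, none of them given in the documents:
- The planned 45/30/10% are the rates when users count as failures.
- A share r of each arm uses a prohibited AD treatment and has an observed Week 8 value.
- A share q = 25.5% of these are then scored as successes. The figure is borrowed from the triamcinolone (TC) arm of the Phase 2 study in Protocol 2.2.2.4.1, where 1.5% BID was "more efficacious than TC by IGA response at Week 4: 38% versus 25.5" (percent).

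Observed rate = p + r × q. For example, vehicle at r = 20%: 0.10 + 0.20 × 0.255 = 0.151.

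| r vehicle / r active | Vehicle | 0.75% | Difference (points) | Power, 0.75% |
|---|---|---|---|---|
| 0 / 0 | 10.0% | 30.0% | 20.0 | 98.9% |
| 5% / 2% | 11.3% | 30.5% | 19.2 | 97.8% |
| 10% / 3% | 12.6% | 30.8% | 18.2 | 95.7% |
| 20% / 5% | 15.1% | 31.3% | 16.2 | 87.5% |

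For 1.5%, power stays above 99.9% in every row. With q varied from 20% to 40% over the same range of r, the 0.75% difference runs from 19.4 to 14.0 points and its power from 98.1% to 72.2%; for 1.5%, power is still at least 99.9%.

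**4. Illustration for PP.** If every user would have failed and is deleted, the rate becomes p / (1 − r).
- r = 5% / 2%: 30.6% − 10.5% = 20.1 points.
- r = 10% / 3%: 30.9% − 11.1% = 19.8 points.
- r = 20% / 5%: 31.6% − 12.5% = 19.1 points.

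Against 20 points, the 0.75% contrast moves by +0.1 to −0.9.

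**The case against.** **The Protocol already handles treatment failure.** Sections 6.5.2 and 10.4.1 together make a participant whose AD requires a prohibited medicine a nonresponder. That is a fair reading of the Protocol. But the SAP governs the analysis and leaves out the clause, and the clause never reached users who stay on study drug.

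**The bias is conservative, and scoring observed values is a legitimate treatment-policy choice.** The first part stands where use is heavier on vehicle: dilution does not manufacture superiority. The second would stand if the plan declared that strategy. It does not, and it departs from the Protocol unannounced.

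**The illustration rests on weak inputs.** This stands. The only nearby evidence is that 1 of 307 participants in the Phase 2 study stopped for lack of efficacy, which is not a rate of prohibited treatment but gives no support to 20%. The 25.5% comes from four weeks of assigned triamcinolone from baseline, not from late use in failing participants, and the Protocol does not say that IGA response there means IGA-TS.

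Three stronger readings are tempting and not supported:
- *Users are never counted as failures.* Those with a missing value or an observed nonresponse are.
- *The PP analysis is seriously distorted.* Once both arms are adjusted, the shift is under one point on the same assumptions.
- *SAP 6.3 removes compliant users of restricted products.* The item sits in a list of important protocol deviations, and use within the Protocol 6.6.2 conditions is not a deviation. The missing qualifier is a wording matter in a supportive set.

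**Conclusion.** The point holds as an undeclared conflict between Protocol 10.4.1 and SAP 4.1.5/7.2.2, together with a gap on prohibited AD treatment. It concerns only users with an observed Week 8 success, who count as responders in the primary and key secondary ITT analyses. If use is commoner on vehicle, the treatment difference is understated. By how much cannot be known from the documents. The illustrated loss falls on the 0.75% dose, and with a 25.5% response after use only the heaviest scenario takes its power below 95%; the 1.5% conclusion is insensitive throughout. It should be corrected before database lock, because the intended rule is cheap to state and affects the primary endpoint's definition of response. It is not a threat to the validity of a positive superiority result under that pattern of use.

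**What to change.** - **SAP 4.1.5, 7.2.2 and 7.3.2:** restore the Protocol 10.4.1 discontinuation clause. If its removal is intended, list it in SAP 10.1 and say whether an early EOT value may serve as Week 8.
- **Same sections:** count a participant who uses a Protocol 6.6.3 AD treatment between Day 1 and Week 8 as a nonresponder from first use. Identify such use under blind from the concomitant medication eCRF before lock.
- **Sensitivity:** keep the analysis of observed values regardless of such use.
- **Minor wording, SAP 6.3:** limit the restricted item to use outside the conditions in Protocol 6.6.2. Whether prohibited-treatment users belong in the PP set is debatable, and no change is needed there.

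Cost: a few sentences and one blinded medication review. The data are already collected (Protocol 6.6) and concomitant medications are already to be summarised for the vehicle-controlled period (SAP 6.6), so nothing new is gathered. The downside is that response rates may fall slightly.
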